### 7.3 LOST TO FOLLOW-UP

A participant will be considered lost to follow-up if he or she fails to return for a visit within a 6 month time frame and is unable to be contacted by the study site staff.

The following actions will be taken if a participant fails to return to the clinic for a required study visit:

- The study coordinator will attempt to contact the participant and reschedule the missed visit within 2 weeks and counsel the participant on the importance of maintaining the assigned visit schedule and ascertain if the participant wishes to and/or should continue in the study.
- Before a participant is deemed lost to follow-up, the investigator or designee will make every effort to regain contact with the participant (3 telephone calls and, if necessary, a certified letter to the participant's last known mailing address). These contact attempts will be documented in the participant's medical record or study file.
- Should the participant continue to be unreachable, he or she will be considered to have withdrawn from the study with a primary reason of lost to follow-up.
- If a participant is reachable but is unable to come in person for the study visit, a telephone interview will be conducted with the participant and an informant to assess the secondary end point of dementia / MCI.

## 8 STUDY ASSESSMENTS AND PROCEDURES

### 8.1 EFFICACY ASSESSMENTS

#### **Screening assessment**

Screening for eligible participants will be performed using the Mayo medical records by a study coordinator. Only patients who have previously given consent to the use of their medical records for research purposes will be screened. ECG, Holter, telemetry recordings will be reviewed to confirm the diagnosis of AF. Charts will be reviewed to assess eligibility for the study including past medical history, current medications, laboratory tests and calculation of the CHA2DS2-VaSC score. The creatinine will be checked if a measurement within 3 months of enrollment is not available.

Potential participants will be contacted in person or through a letter or on the phone. Interested persons will be interviewed on the phone to confirm eligibility and will have a blood test for creatinine if needed. Once enrolled, subjects will be randomized to one of the study arms and will start study drug.

Baseline assessment of brain MRI will be performed prior to initiation of study drug. Baseline assessment of cognitive function will be performed prior to or within 1 month of enrollment. Subsequent assessments will be performed at 1 and 2 year follow-up or within a 3 month time frame of this date.

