### 5.4 SCREEN FAILURES

Screen failures are defined as participants who consent to participate in the clinical trial but are not subsequently randomly assigned to the study intervention or entered in the study. An example of a screen failure is someone who is diagnosed with newly recognized dementia or intracerebral hemorrhage following the administration of the baseline neurocognitive assessment and brain MRI. Information on screen failures will be collected for purposes of reporting as follows: demography, eligibility criteria, reason for screen failure and any serious adverse event.

Individuals who do not meet the criteria for participation in this trial (screen failure) will not be rescreened.

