## 7 STUDY INTERVENTION DISCONTINUATION AND PARTICIPANT DISCONTINUATION/WITHDRAWAL

### 7.1 DISCONTINUATION OF STUDY INTERVENTION

Discontinuation from study intervention (anticoagulant use) does not mean discontinuation from the study, and remaining study procedures should be completed as indicated by the study protocol. If a clinically significant finding is identified (including, but not limited to changes from baseline) after enrollment, the investigator or qualified designee will determine if any change in participant management is needed. Any new clinically relevant finding will be reported as an adverse event (AE). Events that may trigger include:

1. Major bleeding event. The anticoagulant will be discontinued and future management of anticoagulant will be decided by the treating physician. The patient will not be re-challenged with anticoagulant as part of the study protocol.
2. Ischemic Stroke / TIA. Management of anticoagulant in the first month following an ischemic stroke / TIA will be determined by the treating physician. Following this, a decision regarding whether to continue study intervention will be made in consultation with the treating physician and the patient. Whether the anticoagulant was being used in a therapeutic fashion at the time of event will be part of this discussion.
3. Hemorrhagic stroke. The study intervention will be discontinued and future anticoagulation decision will be made by the treating physician.
4. Participants will be strongly encouraged by the study staff to remain on treatment assigned through randomization and to comply with the study protocol and follow-up. However, participants or their physician may voluntarily discontinue study intervention or change OAC treatment at any time. Study staff will make every effort to discourage this.

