Participants who change OAC treatment during follow-up will be withdrawn from the study. A CRF will collect details of the reason for discontinuation of study intervention. Endpoints will be assessed at the time of withdrawal from the study including MRI and cognitive function. The MRI of the head and / or cognitive assessment will be performed at the time of withdrawal from the study if it is greater than 6 months since their last assessment of MRI and / or cognitive function. If a patient withdraws within 6 months of the last assessment, repeat testing will not be performed and the last assessment will be used for the analysis. Participants who withdraw from the study will be followed for 30 days after withdrawal for adverse events. A primary intention to treat analysis will be performed at the end of the study. Participants who withdraw or change OAC treatment will be censored at the time of withdrawal.

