### **Brain MRI imaging to assess burden of cerebral infarcts and cerebral microbleeds**

#### **MR Imaging of brain**

Cerebral MRI will be performed *without* gadolinium contrast using a 3 Tesla scanner at enrollment and at 2 years. If a subject is withdrawn or withdraws prior to the completion of follow-up, an attempt to obtain MRI prior to withdrawal will be made. The following imaging sequences will be performed per standard protocols at our institution: (1) sagittal T1-weighted, (2) axial T2-weighted fast spin echo (FSE), (3) axial T2-weighted fluid-attenuated inversion recovery (FLAIR), (4) axial gradient echo (GRE), (5) axial diffusion tensor-tracer imaging (DTI), (7) 3-dimensional magnetization prepared rapid gradient-echo (MPRAGE) sequence and (8) Axial SWAN (T2 Star Weighted Angiography).

The MRI will be read by a board certified Radiologist who is blinded to treatment assignment.

A new cerebral infarct will be defined as an unequivocal focus of hyperintensity to gray matter on DTI images. GRE and MPRAGE sequences will be used to quantitate the cerebral microbleeds. Cerebral volume analysis will be performed for total cerebral and hippocampal volume using standardized software. The number, size and location of new cerebral infarcts (cortical vs. subcortical and specific anatomic location of infarct) and cerebral microbleeds (lobar vs subhemispheric and specific anatomic location of infarct) will be determined and documented in a CRF.

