#### 8.3.11 REPORTING EVENTS TO PARTICIPANTS

Study participants will be informed of any adverse events or incidental findings through a letter or phone call. In the case of a serious adverse event, the participant will be informed through a phone call within 48 hours of the occurrence. If patient is not reachable, attempts will be made to reach the alternative contact person and the primary treating physician, whose contact information will be sought from the subject at enrollment. The participant will be encouraged to seek care with the primary

treating physician to treat SAEs and to assess any incidental findings, such as findings on brain imaging that require further assessment.

Interpretation of the brain MRI will be performed by a board certified clinical Radiologist and a report generated in the patient's clinical record. This report will be shared with the participant through a letter. This report is however different from the more detailed analysis of the sequences that will be performed by the study Radiologist in a blinded fashion. The results of the cognitive function testing will be shared with individual participants only in the event of diagnosis of dementia, which is expected to have an impact on the overall management of the subject. The aggregate results of the study will be shared with all the participants once published in a peer review journal.

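### The baseline MRI is not clearly placed before randomisation, so an exclusion it reveals can be applied, and the participant replaced, with the arm known

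*Combined protocol and SAP*

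**What the plan says.** - **Section 8.1, Screening assessment.** The sequence is "Once enrolled, subjects will be randomized to one of the study arms and will start study drug". The scan is then bounded only by the last step: "Baseline assessment of brain MRI will be performed prior to initiation of study drug".
- **Section 8.1, MR Imaging of brain.** The scan is done "using a 3 Tesla scanner at enrollment and at 2 years", with no order given relative to randomisation.
- **Section 6.3.** The randomisation code is generated at enrolment and is used to label the scan. The participant, principal investigator and coordinator know the arm; those who read the endpoints do not.
- **Section 5.4.** Screen failures are people who consent but "are not subsequently randomly assigned to the study intervention or entered in the study". One example given is an intracerebral haemorrhage recognised after the baseline MRI.
- **Section 5.2, item 9.** Prior severe bleeding, including intracranial haemorrhage, is an exclusion. Microbleeds and silent infarcts are not listed.
- **Section 7.2.** The investigator may withdraw a participant who turns out to meet an exclusion that had not been recognised before. Those randomised but never treated may be replaced.
- **Section 9.3.** The intention-to-treat set is everyone randomised.

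**The concern.** Whether a person enters the trial should be settled before anyone can know the arm. Section 5.4 assumes this for the baseline MRI, but section 8.1 does not require it. Under 8.1 a site could randomise, disclose the arm, scan, and only then learn that the participant has an exclusion.

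The decision to keep or withdraw that person would be made by an unblinded investigator under a permissive rule, and a replacement could be recruited. If the decision is influenced by the allocated drug, the arms stop being comparable on a feature that the protocol's own background ties to cognition. Replacement restores the head count but not the comparison that randomisation protected.

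**Working it through.** **1. The plan's own figures.** Section 9.2 gives a difference of 0.05 per year, SD 0.16, one-sided alpha 0.05 and 140 per arm. Power = Φ(0.05 / (0.16·√(2/140)) − 1.645) = Φ(2.615 − 1.645) = 83.4%, which agrees with the stated figure of over 80%. Screen failure of 20% gives 140/0.8 = 175 per arm and 280/0.8 = 350 in total, as stated. Section 9.2 counts the 175 within each arm, although under 5.4 a screen failure is never assigned to an arm. That wording does not settle the order either.

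**2. The order, section by section.**

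| Section | Places the baseline MRI |
|---|---|
| 8.1 Screening assessment | before first dose; may fall after randomisation |
| 8.1 MR Imaging of brain | at enrolment; order not given |
| 6.3 | labelled with a code that is generated at enrolment |
| 5.4 | before randomisation, by implication |

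A scan before randomisation satisfies every row. A scan between randomisation and first dose satisfies 8.1 but not 5.4. Section 5.4 cannot be relied on to override 8.1. Its other example is dementia found at the baseline cognitive assessment, and section 3 allows that assessment up to one month after randomisation.

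**3. What follows if 8.1 is applied.** Allocation is known (6.3); the MRI shows an item 9 exclusion (5.2); the investigator may withdraw the participant, and an untreated one may be replaced (7.2). The set analysed may then no longer be the set randomised (9.3).

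**4. Illustration of size.** The documents give neither the rate of MRI-revealed exclusions nor the rate of decline in such people. Assume that an excess share s of one arm is removed without replacement, that those removed decline D per year faster than that arm's mean, and that the SD stays at 0.16. The retained mean shifts by s·D/(1−s), with SE = 0.16·√(1/140 + 1/(140(1−s))). Power, with the loss in the warfarin arm, is Φ((0.05 − shift)/SE − 1.645). Type I error, with the loss in the apixaban arm and no true effect, is Φ(shift/SE − 1.645).

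| s (number of 140) | D | Shift per year | Power, loss from warfarin | Power, same loss without selection | One-sided type I error, loss from apixaban |
|---|---|---|---|---|---|
| 2% (2.8) | 0.08 | 0.0016 | 80.8% | 83.1% | 5.9% |
| 5% (7) | 0.08 | 0.0042 | 76.4% | 82.5% | 7.7% |
| 10% (14) | 0.08 | 0.0089 | 67.3% | 81.6% | 11.7% |
| 2% (2.8) | 0.16 | 0.0033 | 78.4% | 83.1% | 7.0% |
| 5% (7) | 0.16 | 0.0084 | 69.2% | 82.5% | 11.3% |
| 10% (14) | 0.16 | 0.0178 | 49.8% | 81.6% | 23.0% |

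The harm comes from selection, not from lost numbers. Only the excess of one arm over the other counts as s, so the lower rows would need frequent, strongly arm-dependent exclusion.

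**The case against.** **The order may already be as it should be.** Section 5.4 implies it, 8.1 is compatible with it, and the schema and the Schedule of Activities cited in section 4.3 are not shown in the public text and may state it. This stands as far as it goes: it would be wrong to say that the plan places the MRI after randomisation. The finding is that the sections disagree on what is permitted.

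**A baseline finding precedes treatment, so excluding on it need not bias anything.** That is true when the exclusion is applied alike in both arms by someone who does not know the arm. Section 7.2 gives the decision to an unblinded investigator and makes it discretionary.

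**A stronger reading is tempting.** The clinical MRI report enters the chart, and "This report will be shared with the participant through a letter" (8.3.11). Under 7.1, "participants or their physician may voluntarily discontinue study intervention or change OAC treatment at any time", and then "Participants who change OAC treatment during follow-up will be withdrawn from the study". A reader might infer that late scanning lets MRI reports drive high-risk patients out of the warfarin arm. The documents do not support that:

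- The report stays in the chart and the arm becomes known whenever the scan is done, so scan timing neither opens nor closes this route. The bias would come from the rule in 7.1 that withdraws and censors switchers, which conflicts with the intention-to-treat statement in the same section.
- The direction is inference. Section 2.2 links vitamin K antagonists to microbleeds, but its apixaban comparison is with aspirin, and it says that anticoagulation in general raises bleeding risk in the brain. Staff are also told to discourage switching.
- Any size is invented. Suppose 20–30% have baseline microbleeds, 10–30% of these leave the warfarin arm and none leave apixaban, with two-year new-microbleed risks of 40% and 8%. The warfarin risk then moves from 14.4% to 13.9% at one extreme, (0.2·0.9·0.40 + 0.8·0.08)/0.98, and from 17.6% to 15.4% at the other, (0.3·0.7·0.40 + 0.7·0.08)/0.91. That is 0.5 to 2.2 percentage points, against a standard error of the difference of about 4.2 to 4.6 points. No input is in the documents.

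A reader might also infer that the MRI has no time limit for existing warfarin users allocated to warfarin, because they start no new drug. The MRI section sets the scan at enrolment for everyone, so this does not hold.

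**Conclusion.** The concern holds in a narrow form. Sections 5.4, 6.3 and 8.1 do not agree on whether the baseline MRI and its eligibility review precede randomisation. Read with 7.2, the looser wording in 8.1 allows exclusion and replacement after allocation by someone who knows the arm. That is a route to selection bias in a set meant to contain everyone randomised.

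Its size cannot be derived from the plan. It depends on how often the scan reveals an exclusion, how unequally the exclusion is applied, and how different those people are. At a 2–5% excess in one arm and D = 0.08 the effect is small but not nil. The direction is unknown: loss of fast decliners from warfarin works against apixaban, and loss from apixaban works in its favour. This is worth correcting mainly because prevention is cheap. It is not evidence that the result would be wrong.

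**What to change.** 1. **Section 8.1:** state that the baseline MRI has been done, and its clinical read reviewed against section 5.2, before the allocation is generated.
2. **Sections 5.4, 6.3 and MR Imaging of brain:** align them with that order. In 6.3, separate the identifier on the scan from the allocation. Replace the enrolment time point with one defined relative to randomisation. The same decision is needed for the baseline cognitive assessment, which 5.4 also uses to define screen failures.
3. **Section 7.2:** do not replace participants once randomised. Anyone whose exclusion is found later stays in the set in 9.3.
4. **Section 9.2:** describe the 350 as people who consent and the 280 as those randomised, instead of counting screen failures within arms.

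The cost is protocol wording and a few days between scan and randomisation. No extra scans are needed if 5.4 already describes practice, and 140 per arm with 83.4% power is unchanged.

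Handle separately the switching rule in 7.1: follow and analyse all randomised participants whether or not they change anticoagulant, and record the reason for and timing of each change by arm and MRI finding. Moving the scan does not do this.

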### 3 OBJECTIVES AND ENDPOINTS

OBJECTIVES	ENDPOINTS	JUSTIFICATION FOR ENDPOINTS
Primary		

To assess the change in global cognitive function using standardized neurocognitive assessment in patients with atrial fibrillation over the age of 60 years with CHA2DS2-VASc score <math>\geq 2</math> treated with Apixaban versus warfarin
	
The individual cognitive domain and global cognitive function score using a battery of standardized neurocognitive function tests (presented below in detail).
 
 
○ All enrolled subjects will undergo assessment of cognitive function at (1) before or within 1 month of randomization (2) 1 year and (3) 2 years.
 
	
Cognitive function scores are chosen as the primary end point due to their sensitivity to detect changes in cognitive function within a short span of time. While dementia is also an important end point, it is increasingly recognized that milder degrees of cognitive dysfunction are more prevalent and may have an important impact on a person’s quality of life and morbidity. Early recognition of cognitive decline can lead to earlier intervention to either treat or prevent progression. Hence the primary end point of decline in cognitive function in one or more domains will be a clinically relevant and a patient centered outcome.
 
Additionally, AF may have a greater impact on non-memory cognitive domains such as executive function, thus predisposing to non-amnesic dementia. Hence we will test individual cognitive domains to

OBJECTIVES	ENDPOINTS	JUSTIFICATION FOR ENDPOINTS
		increase the sensitivity of the tests.
Secondary		

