### **5.2 EXCLUSION CRITERIA**

An individual who meets any of the following criteria will be excluded from participation in this study:

1. Patients who are not a candidate for oral anticoagulation as assessed by a treating physician including the presence of active bleeding.
2. Prior treatment with Apixaban for >1 month. (Prior exposure to warfarin or novel direct oral anticoagulants other than Apixaban is not an exclusion criterion).
3. Known hypersensitivity to warfarin or Apixaban.
4. CHA2DS2-VASc score <2

5. Valvular AF defined as history of rheumatic valve disease, moderate or greater mitral stenosis, and presence of a mechanical cardiac valve.
6. Need for dual anti-platelet therapy with aspirin and another agent such as a thienopyridine.
7. Aspirin monotherapy with doses > 100 mg if the patient is unable to reduce the dose to <100 mg.
8. Severe renal insufficiency (serum creatinine level of >2.5 mg/dl or calculated creatinine clearance of <25 ml/minute) or dialysis.
9. Prior severe bleeding including intracranial hemorrhage and GI bleed requiring transfusion.
10. Recent stroke (within 7 d)
11. Known diagnosis of dementia or dementia diagnosed at first evaluation.
12. Presence of MRI non-compatible implanted devices including cardiac implantable electronic devices. Patients with MRI conditioned cardiac implantable electronic devices will also be excluded. This is done in light of concerns regarding patient safety in MRI scanner.
13. Inability to undergo MRI due to claustrophobia.
14. Current or expected systemic treatment with strong dual inducers of CYP3A4 and P-gp (e.g., rifampin, carbamazepine, phenytoin, St. John's wort) because such drugs will decrease exposure to apixaban
15. Current or expected systemic treatment with strong dual inhibitors of CYP3A4 and P-glycoprotein (e.g., ketoconazole, itraconazole, ritonavir, or clarithromycin) in patients who would qualify for Apixaban dose of 2.5 mg BID.
16. Currently enrolled in another investigational device or drug trial that has not completed the primary endpoint or that clinically interferes with the current study endpoints.
17. Co-morbid condition(s) that could limit the subject's ability to participate in the trial or to comply with follow-up requirements, or that could impact the scientific integrity of the trial.

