### 6.3 MEASURES TO MINIMIZE BIAS: RANDOMIZATION AND BLINDING

Study participants will be randomized 1:1 to either Apixaban or dose adjusted Warfarin. Placebo pills will not be administered. Participants, the principal investigator and study coordinator will not be blinded to treatment assignment. Study personnel administering and interpreting the MRI images and cognitive function assessment will be blinded to treatment assignment. Randomization codes will be generated at the time of enrollment and each individual's cognitive function tests and MRI scan identified by this code. Blinding of participants in this study will require the use of placebo and INR testing in both groups, which will be burdensome to the patient and will not affect the outcomes of cognitive function or MRI findings.

Unblinding of personnel to treatment assignment will be performed only when there is a serious adverse event such as intra-cranial hemorrhage.

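### The baseline cognitive test may follow open-label randomisation by up to 1 month, although dementia found at that test is an exclusion and a screen failure

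*Combined protocol and SAP*

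**What the plan says.** **Timing.** The endpoint table in Section 3 places the first cognitive assessment "before or within 1 month of randomization". Section 8.1 (screening assessment) says "Baseline assessment of cognitive function will be performed prior to or within 1 month of enrollment" and gives the sequence: "Once enrolled, subjects will be randomized to one of the study arms and will start study drug". The rule for imaging is stricter: "Baseline assessment of brain MRI will be performed prior to initiation of study drug". The primary-endpoint paragraphs of Sections 8.1 and 9.1 give enrolment as the first time point and no window.

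**Eligibility.** Exclusion 11 in Section 5.2 reads "Known diagnosis of dementia or dementia diagnosed at first evaluation". Section 5.4 defines screen failures as "participants who consent to participate in the clinical trial but are not subsequently randomly assigned to the study intervention or entered in the study" and gives as its example "someone who is diagnosed with newly recognized dementia or intracerebral hemorrhage following the administration of the baseline neurocognitive assessment and brain MRI".

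**Knowledge of the arm.** Section 6.3: "Participants, the principal investigator and study coordinator will not be blinded to treatment assignment". The same section blinds the staff who give and interpret the cognitive tests. Sections 8.1 and 9.1 blind the team that assigns the diagnosis.

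**After randomisation.** Section 7.2 allows an investigator to withdraw someone who meets an exclusion that was not recognised before. Section 7.1 keeps a person who stops study drug in follow-up, but orders no repeat test for someone who withdraws within 6 months of the last assessment. Section 9.3 defines the ITT set as everyone randomised.

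**The concern.** Sections 5.2 and 5.4 make sense only if the baseline cognitive evaluation comes before randomisation. Sections 3 and 8.1 allow it afterwards. For anyone tested in that later window, eligibility on dementia is settled when the arm is already known to the participant, the principal investigator and the coordinator, and the decision to withdraw is discretionary.

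Two things are at stake. First, participants with unrecognised dementia may decline faster than the others. If they were withdrawn more readily from one arm, the slope comparison would lose some of the protection of randomisation. Second, the reference score for the primary endpoint may be taken after study drug has begun, which the protocol does not allow for the MRI.

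**Working it through.** **1. The same person under the two permitted timings.**

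| | Tested before randomisation | Tested up to 1 month after |
|---|---|---|
| Dementia found: exclusion (5.2)? | Yes | Yes |
| Matches the example in 5.4? | Yes | Yes |
| Meets the definition in 5.4? | Yes | No, already randomised |
| In the ITT set (9.3)? | No | Yes |
| Who decides what follows? | The eligibility rule | An investigator, at discretion (7.2) |
| Arm known to the principal investigator? | No arm exists | Yes (6.3) |
| Cognitive scores if withdrawn at that point | Not applicable | One (7.1) |

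The alternative limb of the definition, not being entered in the study, does not rescue the right-hand column. Under Section 8.1 that person has been enrolled and randomised.

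**2. The plan's own figure.** Section 9.2 gives a difference of 0.05/year, SD 0.16, 140 per arm, and one-sided alpha 0.05.

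- Standard error: 0.16 × √(2/140) = 0.0191.
- 0.05 / 0.0191 = 2.61, and 2.61 − 1.645 = 0.97, so power is 83.4%.

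This agrees with the stated power of more than 80%.

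**3. Power if late-found cases are lost evenly from both arms.** The documents give no rate of dementia at the first test, so the rates are assumed.

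| Share of 280 removed | People (about) | Power |
|---|---|---|
| 1% | 3 | 83.1% |
| 2% | 6 | 82.7% |
| 5% | 14 | 81.7% |
| 10% | 28 | 79.8% |

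Power is not the issue unless losses approach 10%.

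**4. Bias if the loss is uneven.** Let k be the net excess of people lost from one arm, each declining m SDs per year faster than the rest of that arm. If a person with a single score adds nothing to the slope, the shift is (k/140) × m × 0.16. Both k and m are assumed.

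- k = 0 (balanced loss): 0.
- k = 2, m = 1: 0.0023/year, or 4.6% of 0.05.
- k needed for a shift of 10% of the target (0.005/year): 0.005 × 140 / 0.16 = 4.4 people at m = 1, or 0.005 × 140 / 0.32 = 2.2 people at m = 2.

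**5. The delay itself.** If the mixed model uses actual test times and the treatment effect is linear in time, a late baseline does not bias the slope difference. It costs a little precision:

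- times 0, 1, 2 years: sum of squares about the mean = 2.00;
- times 1/12, 1, 2 years: 1.84;
- 2.00 / 1.84 = 1.088, and √1.088 = 1.043.

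The within-person part of the slope standard error widens by at most 4.3%, and only if everyone were tested a full month late.

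**The case against.** The intended order can be discerned. Section 5.4 puts the baseline evaluation ahead of randomisation or entry, and enrolment is not defined. If it means consent, the window in Section 8.1 alone is compatible with testing before randomisation. Known dementia is excluded and charts are reviewed first, so only unrecognised cases in people who happen to be tested late are affected. The diagnosis is made blind, and one exclusion applies to both arms. Section 7.2 foresees an exclusion that surfaces late, Section 9.3 already keeps all randomised people in the ITT set, and Section 7.1 continues follow-up when only study drug is stopped, so a late diagnosis need not leave a single score.

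Most of this stands, and it limits the consequence. It does not remove the conflict. Section 3 counts its window from randomisation in plain terms, whatever enrolment means. Blinding protects the diagnosis but not the withdrawal decision. Section 7.2 supplies a discretionary route without saying how such a case is classified or analysed. The Schema (1.2) and the Schedule of Activities (cited as 1.3) are not in the text available for this review. They may show the order, but Sections 3 and 8.1 would still need correcting.

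A reader might also take the accrual of 175 in each arm in Section 9.2 as a sign that screen failures are expected after allocation. The documents do not support that: 140/0.8 = 175 and 350 × 0.8 = 280, in agreement with Section 5.5.

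**Conclusion.** The conflict is real: Section 3, and Section 8.1 on its natural reading, permit an eligibility test after open-label allocation that Sections 5.2 and 5.4 treat as coming before it. It deserves correction because the remedy is cheap and following the plan as written is worse.

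A reader might infer that the treatment comparison will be biased, or that late testing is the rule. The documents support neither. Late testing is an option, and randomisation should spread undiagnosed dementia evenly, so nil bias is the expected case. The size of any bias cannot be derived from the documents; the shifts in step 4 rest on assumed numbers of people and assumed rates of decline. A baseline taken after drug start has little effect on the slope estimate, given actual test times and a linear effect. The case therefore rests on the contradiction and on avoidable decisions after allocation, not on a demonstrated bias.

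**What to change.** Use one anchor, randomisation, in Sections 3, 8.1 and 9.1, and replace the window wording with: *Baseline cognitive assessment and the dementia determination will be completed after consent and before randomisation.* Striking out the one-month allowance alone would not be enough, because Section 8.1 would still count from enrolment.

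For anyone nevertheless found ineligible after randomisation, reconcile Section 7.2 with Sections 7.1 and 9.3, so that the person stays in the ITT set and is asked to continue the scheduled cognitive tests.

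The cost is amendment wording and visit order; no test is added. The downside is that randomisation may have to wait for the test appointment and the dementia determination.
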